### Study design:

This is a collaborative study developed by different health and research institutions. The group is composed by BCNatal (Barcelona Center for Maternal Fetal and Neonatal Medicine, *Hospital Sant Joan de Déu*), *Grupo de investigación Infancia y Entorno* (GRIE), Psychiatry Service of *Hospital Clínic de Barcelona* and the Health Department of Catalunya and ASSIR (*Centre d'Atenció a la Salut Sexual i Reproductiva*) of Baix Llobregat.

This is a cluster randomized simple masking controlled trial evaluating the effectiveness of repeated motivational interview (MI) during pregnancy on prevalence of ethanol intake, together with its effects on offspring neurodevelopment.

Data will be collected by the study-site manager and stored in an electronic data-capture database. The coordinator of the study and the statistician will witness the accuracy of the data at the beginning, middle, and end of the study (on-site audit). Data will be captured in a paper form basis and then captured into the electronic database.

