#### Sample size

Assuming a prevalence of ethanol consumption in our environment of at least 40% in the control group and about 25% (or less) in the intervention group. Thus, about 240 of prenatally exposed children will be followed up in their postnatal period. According to previous experience cohort studies, we may assume a maximum of 30% of loss during their ambulatory control. Regarding this estimate, 168 children will complete their follow up. This sample size can ensure a 90% of potency to detect differences of prevalence between both groups, with a signification of 5%.

Values were corrected regarding number of clusters (n= 8) and intraclass correlation coefficient. Intraclass correlation coefficient was estimated regarding the prevalence of ethanol intake among groups.

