### Randomization and intervention

Under a sequential rollout, 8 clusters (primary care centers from a geographic location of Barcelona; Baix Llobregat) were randomly allocated according to a random number generator with a fixed seed, using R Core Team (2018). R: A language and environment for statistical computing. R Foundation for Statistical Computing, Vienna, Austria. URL <https://www.R-project.org/>, to incorporate a MI program into existing prenatal care visits (intervention group) or usual intervention (control group). The allocation was performed by a statistician. Midwives from centers allocated to perform MI were trained by an expert team. Participants enrolment was performed by midwives of both groups (interventional and control group). This is a simple masking study, it means that participants will not aware of the allocation and intervention.

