### Statistical analysis

Analysis will be conducted by intention-to-treat. Missing data for the main outcome will be handled by complete data analysis because women without an answer on the main outcome will be excluded. All analyses will be divided by groups (control vs experimental group). Continuous data will be assessed for normality using the Kolmogorov-Smirnoff test. Normally distributed variables will be compared among groups using t-test and expressed as mean and standard deviation (SD), while not normally distributed variables will be compared using the Mann-Whitney-U test and expressed as medians and interquartile range (IQR). Quantitative variables will be compared using  $\chi^2$  test and expressed as counts (n) and proportions (%). For categorical variables Fisher exact test or Chi-squared test are used. Regarding demographic data (age, sex, body mass index (BMI), etc.); continuous variables will be presented as mean and SD, or median and IQR, according to their distribution, and categorical variables as percentages (%).

For the main outcome, differences in prevalence of ethanol intake between groups will be analyzed using absolute risk increase defined as the incidence of the outcome in the experimental group minus the incidence in the control group. The absolute risk increase will be depicted in a forest plot. A multivariate logistic regression will be performed to determine the Odds Ratio for ethanol intake adjusting by demographic characteristics. Data will be analyzed using R Core Team (2018). R: A language and environment for statistical computing. R Foundation for Statistical Computing, Vienna, Austria. URL <https://www.R-project.org/> and GraphPad Prism version 8.1.2, GraphPad Software, San Diego, California USA, [www.graphpad.com](http://www.graphpad.com).

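### Eight centres are randomised, but the planned between-arm tests treat women as independent, so the 5% type I error is not held

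*Combined protocol and SAP*

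**What the plan says.** The Study design section states: "This is a cluster randomized simple masking controlled trial". The Randomization and intervention section confirms the unit: "8 clusters (primary care centers from a geographic location of Barcelona; Baix Llobregat) were randomly allocated". How the eight divide between arms is not stated.

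The Sample size section allows for clustering: "Values were corrected regarding number of clusters (n= 8) and intraclass correlation coefficient". It says an ICC was estimated but gives no value, cluster size or design effect.

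The Statistical analysis section is the only place where analysis methods are named. Continuous variables get a t-test or Mann-Whitney test. On categorical variables it says: "For categorical variables Fisher exact test or Chi-squared test are used". The main outcome is summarised as a difference in prevalence, with no variance or interval method, and then modelled: "A multivariate logistic regression will be performed to determine the Odds Ratio for ethanol intake adjusting by demographic characteristics". No section mentions a random effect for centre, GEE, cluster-robust variance, a centre-level summary, or an allowance for the small number of clusters.

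**The concern.** Women at one centre share midwives, catchment and, in the intervention arm, the same trained staff, so their outcomes are likely to be more alike than those of women at different centres. The intervention effect is then estimated from differences between eight centres. A method that counts each woman as an independent unit takes its standard error only from variation between women and ignores variation between centres.

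The intervals come out too narrow and the p-values too small. An ordinary difference between centres, unrelated to motivational interviewing, can be declared an intervention effect. That matters because the protocol presents the intervention as a candidate for a public healthcare programme. The same applies to the other between-arm comparisons, including offspring neurodevelopment.

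**Working it through.** **The plan's own figure.** Inputs from the Sample size section are prevalences of "at least 40% in the control group and about 25% (or less) in the intervention group", 240 followed up, 30% loss, 90% power and 5% significance. The loss arithmetic is right: 240 × 0.70 = 168. The power claim does not reproduce if 168 is the total. With 84 per arm, two-sided 5% and no clustering:

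power = Φ{[0.15√84 − 1.96√(2 × 0.325 × 0.675)] / √(0.40 × 0.60 + 0.25 × 0.75)} = Φ(0.117) = 54.7%.

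Ninety per cent power would need 203 per arm before any design effect. The point below does not depend on this. It is why 168 and 240 are both carried forward.

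**Assumptions.** The documents do not give the ICC, cluster sizes, arm split or sidedness. I take four equal centres per arm, a two-sided test, true prevalence 40% in both arms, and ICC from 0.005 to 0.05.

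**Formulas.** With m women per centre, the design effect is DE = 1 + (m − 1) × ICC. An independence-based standard error is too small by a factor √DE, so the actual type I error of a nominal 5% test is 2 × [1 − Φ(1.96/√DE)].

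Worked case: 168 women, m = 168/8 = 21, ICC 0.02. DE = 1 + 20 × 0.02 = 1.40; √1.40 = 1.18; error = 2 × [1 − Φ(1.96/1.18)] = 9.8%.

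**Results.** The simulations are beta-binomial with 20,000 replicates per setting.

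| Women (per centre) | ICC | DE | √DE | Chi-squared, formula | Chi-squared, simulated | Fisher, simulated |
|---|---|---|---|---|---|---|
| 168 (21) | 0.005 | 1.10 | 1.05 | 6.2% | 5.9% | 4.2% |
| 168 (21) | 0.01 | 1.20 | 1.10 | 7.4% | 7.5% | 5.4% |
| 168 (21) | 0.02 | 1.40 | 1.18 | 9.8% | 10.1% | 7.3% |
| 168 (21) | 0.05 | 2.00 | 1.41 | 16.6% | 17.0% | 14.0% |
| 240 (30) | 0.005 | 1.145 | 1.07 | 6.7% | 6.8% | 5.2% |
| 240 (30) | 0.01 | 1.29 | 1.14 | 8.4% | 9.4% | 7.1% |
| 240 (30) | 0.02 | 1.58 | 1.26 | 11.9% | 12.8% | 9.6% |
| 240 (30) | 0.05 | 2.45 | 1.57 | 21.1% | 21.4% | 18.4% |

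If the 240 are exposed children only, the total would be about 240/0.325 = 738 women, or 92 per centre. That reading is an assumption. The formula then gives 15.6%, 24.4% and 40.6% at ICC 0.01, 0.02 and 0.05. With the number of centres fixed, recruiting more women makes the inflation worse.

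**Centre-level analysis.** A t-test on the eight centre proportions, with 8 − 2 = 6 df, rejected between 4.8% and 5.5% of the time over all simulated settings (168, 240 and 736 women; ICC 0 to 0.10).

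**Why ordinary robust errors are not enough.** With four equal centres per arm, the uncorrected sandwich variance of the risk difference is (4 − 1)/4 = 0.75 of the unbiased centre-level variance. A normal reference therefore rejects when the centre-level |t| exceeds 1.96 × √0.75 = 1.70. On 6 df that has probability about 14%, and simulation also gave about 14%.

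**The case against.** The strongest reply is that the plan is silent on clustering rather than committed to ignoring it, and that the sample size already allows for it. It is true that the plan never declares independence, that a risk difference is an effect measure and not a test, and that the Sample size section shows the authors had clustering in mind. But a larger sample does not alter the standard error formula of an unadjusted test. Nor is centre a demographic characteristic, so the planned adjustment does not bring it in. An analyst following the text would run individual-level tests.

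A second reply is that the inflation may be small. This stands in part. At ICC 0 there is none, and Fisher's test is conservative enough (3.3% with 168 women and 3.8% with 240 at ICC 0) to stay near or below 5% at very low ICC. With 168 women it reaches only 5.4% at ICC 0.01. It does not protect at ICC 0.02 or more, and it offers nothing for the logistic model or the continuous outcomes.

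Third, the Outcomes section labels no secondary endpoint, so the point beyond the primary outcome is properly about the other between-group comparisons. Fourth, the protocol mentions a sequential rollout. If centres started at different times, a simple two-group centre comparison may be incomplete. Both are fair, and the fix allows for them.

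**Conclusion.** The concern holds. The unit of randomisation is the centre, every test and model named for comparing arms assumes independent women in its standard form, and following the text gives invalid inference whenever the ICC exceeds zero by more than a trivial amount. Between ICC 0.01 and 0.05, the true error rate of a nominal 5% chi-squared test is about 7% to 17% with 168 women and 8% to 21% with 240, and standard errors are too small by a factor of 1.10 to 1.57.

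These sizes rest on equal clusters, a 4:4 split and an assumed ICC range. The direction does not. This must be fixed before analysis because it affects the primary conclusion.

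**What to change.** Name a primary analysis that respects the unit of randomisation. Either of these would serve:

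- **Centre-level.** Compare the centres' biomarker-positive proportions between arms with a t-test on 6 df, and report the risk difference with its confidence interval. To keep the demographic adjustment, use two stages: fit the logistic model on demographics without the arm term, then compare the centre-level residuals (observed minus expected) between arms.
- **Individual-level.** Use GEE clustered on centre with a Kauermann-Carroll or Mancl-DeRouen variance and a t reference on 6 df, or a linear mixed model on the risk-difference scale with Kenward-Roger. Kenward-Roger does not apply to GEE and is not routine for a logistic mixed model.

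Use the clustered equivalent for every other between-arm comparison in place of chi-squared, Fisher, t and Mann-Whitney tests. State the arm split and the ICC assumed in the sample size, and report the observed ICC. Explain what the sequential rollout means; if centres entered at different times, add a time term.

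The direct cost is SAP wording and a few lines of R. The real cost is power. For 40% versus 25%, the 6-df test with 168 women has about 37% power at ICC 0.01 (standard error √(1.20 × 0.4275/84) = 0.078, noncentrality 0.15/0.078 = 1.92) and about 24% at ICC 0.05. With 240 women the figures are 46% and 27%. The correction does not create that uncertainty. It is already in the design, and the planned tests would hide it.

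### The planned main analysis is an unadjusted risk difference, and the only adjusted result is an odds ratio of unstated status that cannot be compared with it; one standardised risk difference with centre-level variance would serve better.

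*Combined protocol and SAP*

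**What the plan says.** The Statistical analysis section states that, for the main outcome, "differences in prevalence of ethanol intake between groups will be analyzed using absolute risk increase". This is defined as "the incidence of the outcome in the experimental group minus the incidence in the control group", so benefit is negative, and it is to be shown in a forest plot. No adjustment, test or interval method is attached to it.

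The paragraph continues: "A multivariate logistic regression will be performed to determine the Odds Ratio for ethanol intake adjusting by demographic characteristics". The regression is not called primary, secondary, supportive or sensitivity. Its covariates are not listed. The nearest thing to a list, "Regarding demographic data (age, sex, body mass index (BMI), etc", is open-ended and concerns descriptive presentation. No adjusted risk difference or risk ratio is planned, and the section does not mention centres.

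The Sample size section plans on prevalences of "at least 40% in the control group and about 25% (or less) in the intervention group", with one power statement: 90% power to detect a difference in prevalence "with a signification of 5" per cent. It says the values were corrected for 8 clusters and an intraclass correlation, whose value it does not give.

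**The concern.** There are three linked issues.

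- **Status.** One effectiveness claim is served by two results, and the plan does not say what the regression is for or what happens if the two differ.
- **Scale.** A reader will want to know whether adjustment changed the answer. A crude risk difference set beside an adjusted odds ratio cannot show that: the scale changes together with the adjustment, and an odds ratio moves when a prognostic covariate enters even if the arms are perfectly balanced.
- **Precision.** The trial is planned on a prevalence difference, yet that scale gets no benefit from the baseline data already collected. Nor does its interval, as written, reflect that centres were randomised.

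At stake are the clarity of the main result and the precision and honesty of its interval, and to a lesser degree the error rate.

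**Working it through.** **Plan's own figure.** 240 × 0.70 = 168 reproduces. The 90% power does not: read as total sample sizes, 1:1, two-sided and without clustering, 168 gives 55% and 240 gives 70%. The section counts exposed children rather than randomised women, so its basis is unclear. That is a separate matter and nothing below depends on it.

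**Inputs.** Control 0.40 and intervention 0.25 (Sample size section). Covariate strengths and the total of 412 are assumptions; the documents give neither.

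**Step 1: one effect, three scales.**
- Risk difference: 0.25 - 0.40 = -0.15
- Risk ratio: 0.25 / 0.40 = 0.625
- Odds ratio: (0.25/0.75) / (0.40/0.60) = 0.50

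**Step 2: what a balanced covariate does.** Take a binary predictor present in half of each arm, and hold the overall prevalences at 0.40 and 0.25. Solving for the treatment odds ratio within strata:

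| Covariate odds ratio (assumed) | Conditional treatment odds ratio |
|---|---|
| 3 | 0.478 |
| 5 | 0.454 |
| 8 | 0.427 |

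For covariate odds ratio 5, the stratum prevalences are 0.2179 and 0.5821 in control, and 0.1124 and 0.3876 under intervention.
- Lower-stratum odds ratio: (0.1124/0.8876) / (0.2179/0.7821) = 0.45. The other stratum gives the same.
- Stratum risk differences: 0.1124 - 0.2179 = -0.1055 and 0.3876 - 0.5821 = -0.1945. Their average is -0.150.

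So the odds ratio shifts from 0.50 to 0.45 with nothing wrong in the data, while the standardised risk difference returns exactly -0.15. This is non-collapsibility, not bias.

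**Step 3: false positives if either result may decide.** Simulation with no effect, independent women, and a Wald test of the crude risk difference against a Wald test of the adjusted log odds ratio. Covariate strength is the standard deviation (SD) it contributes on the logit scale. One set of 1,500 runs per setting gave:

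| Covariate SD | Total n | Crude | Adjusted | Either |
|---|---|---|---|---|
| 0 | 168 | 4.7% | 4.7% | 5.2% |
| 0 | 240 | 6.3% | 5.1% | 6.5% |
| 0.5 | 168 | 4.5% | 4.6% | 5.8% |
| 0.5 | 240 | 4.9% | 4.5% | 6.0% |
| 1.0 | 168 | 5.1% | 5.1% | 6.9% |
| 1.0 | 240 | 4.7% | 4.2% | 6.8% |

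The Monte Carlo standard error near 5% is √(0.05 × 0.95 / 1500) = 0.6 points. Across all runs made, the either-significant rate was about 5-7% with weak covariates and 7-8.5% with strong ones.

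**Step 4: disagreement and power under the planned effect.** With 206 per arm (total 412), crude power by formula is Φ[(0.15√206 - 1.96√(2 × 0.325 × 0.675)) / √(0.40 × 0.60 + 0.25 × 0.75)] = Φ[(2.153 - 1.298) / 0.654] = Φ(1.31) = 90%. Simulation with the overall rates held at 40% and 25% gave 90-92% crude, 91-97% adjusted, and disagreement at the 5% level in about 1-7% of trials. At totals of 168 or 240, where power is middling, disagreement was 3-4% with non-prognostic covariates, 7-8% at SD 0.5 and 12-14% at SD 1.0.

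**The case against.** The strongest reply is that the plan already has a main analysis. The risk difference is introduced expressly for the main outcome, is given a direction and a figure, and matches the planning scale; the regression reads as a supplement. That reading is fair. A reader might infer that the plan sets up two rival primary analyses; the text does not support that. What is missing is a label for the regression.

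A reader might also infer that the adjusted odds ratio overstates the effect. It does not: 0.50 is an exact description of 40% versus 25%, and 0.48-0.43 is the correct conditional value under the assumed covariates. It exaggerates only if read as a risk ratio (0.50 against 0.625), and nothing in the documents plans that reading.

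Nor do the figures support a claim of serious error inflation. Under no effect, a risk difference of zero and an odds ratio of one are the same hypothesis, so disagreement comes mainly from adjustment rather than scale, and it is slight if demographics predict alcohol use weakly. The documents do not say how strongly they predict it. The simulations also treat women as independent, so they are not error rates for a trial that randomises 8 centres.

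Finally, naming the crude risk difference as primary would settle the labelling equally well, and an adjusted primary needs a covariate list that the plan lacks. Both points stand. But the crude choice would leave the adjusted result on a scale that cannot be compared, would forgo any precision from data already collected, and would still need a centre-level variance.

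**Conclusion.** The point holds in a limited form. The plan pairs an unadjusted risk difference with an adjusted odds ratio of undefined status, and gives no adjusted result on the scale on which the trial was planned. The two figures cannot be set against each other to judge the effect of adjustment.

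The scale gap (-0.15, 0.625, 0.50) rests only on the plan's own rates. The conditional odds ratios, false-positive rates and disagreement rates rest on assumed covariate strengths, and the simulated rates also on independent women. With no intraclass correlation in the documents, the extra effect of centre-level imbalance cannot be sized. The error-rate consequence is modest. The main reason to act is that a better estimate is available from a model and baseline data already planned.

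**What to change.** State in the Statistical analysis section that the single primary estimate is the risk difference (MI minus control) with a 95% CI, obtained by marginal standardisation: fit the planned logistic model, predict each woman's risk under both arms, average, and subtract. Fix a short list of baseline covariates before analysis. Use a variance that accounts for the 8 randomised centres, with a correction for the small number of clusters. Label the crude risk difference and the odds ratio as supportive, and give the adjusted risk ratio beside the odds ratio so that it is not misread.

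The cost is one paragraph of SAP text and a few lines of R, with no new data or participants. There are downsides. The covariate list must be settled in advance and kept short because there are only 8 centres. The interval will be wider, though honest, once clustering is counted. The precision gained from adjustment will be small if demographics predict alcohol use weakly.

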### Interventions and procedures

For the experimental group, the intervention consists in a MI program during prenatal care visits. MI will be received at least one time each trimester of pregnancy.

For the control group, usual prenatal care attention will be given, but they will be directly asked sign a consent form.

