#### Prenatal procedures:

All participants will be followed-up during the pregnancy applying following procedures:

- Questionnaires to evaluate sociodemographic, health and habits background. This questionnaire will be answered during the first trimester of pregnancy.
- SCL-90 (Symptom Checklist): In order to evaluate mental health. This questionnaire will be filled during the first trimester of pregnancy.
- AUDIT-C (Assessment of the Alcohol use disorders identification test): To evaluate ethanol intake. This questionnaire will be filled during first trimester of pregnancy and also up to 7 days after delivery.
- Fetal neurosonography: To evaluate fetal neurodevelopment and brain structure at 28 and 32 weeks of gestation through transabdominal and transvaginal exploration using a General Electric Voluson E10 sonograph (GE Medical Systems, Zipf, Austria).
- Biological samples: Samples will be collected at the moment of delivery to obtain to different biomarkers :
  - o Ethylglucuronide (EtG) on mother's hair: In order to evaluate chronic ethanol intake.
  - o Phosphatidylethanol (PEtH) on dried cordblood spot: In order to evaluate ethanol intake during last 3 weeks prior delivery.

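### The only adjusted analysis of the main outcome does not name first-trimester AUDIT-C, the one named early drinking measure, as a covariate; adding it is a modest gain if it is taken before MI begins

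*Combined protocol and SAP*

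**What the plan says.** The Statistical analysis section plans two analyses of the main outcome. One is an "absolute risk increase defined as the incidence of the outcome in the experimental group minus the incidence in the control group", with no covariates mentioned. The other is a logistic regression for the odds ratio, "adjusting by demographic characteristics". The only indication of what counts as demographic is an open list: "Regarding demographic data (age, sex, body mass index (BMI), etc".

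Under Prenatal procedures, AUDIT-C is scheduled for all participants to measure ethanol intake: "This questionnaire will be filled during first trimester of pregnancy and also up to 7 days after delivery". The same section lists a separate first-trimester instrument: "Questionnaires to evaluate sociodemographic, health and habits background". AUDIT-C is not mentioned under Outcomes or Statistical analysis, although the general rules for comparing variables between groups would cover a table of it by arm.

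Two other sections matter. On timing, Interventions and procedures says "MI will be received at least one time each trimester of pregnancy", so a session and the early AUDIT-C fall in the same trimester, in no stated order. On recruitment, Randomization and intervention says 8 centres were allocated, describes no stratification, describes masking of participants only, and states "Participants enrolment was performed by midwives of both groups (interventional and control group".

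**The concern.** Among the measures the plan names, first-trimester AUDIT-C is the early one closest to the outcome: self-reported drinking, against biomarkers of drinking at delivery. An adjusted model that uses age or BMI but not early drinking passes over the covariate most likely to be prognostic.

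Two things are at stake. One is precision on the risk difference. The other is protection against selective recruitment. Centres were allocated, women were enrolled by each arm's own midwives, and those in MI centres had been trained for MI. If recruiters knew their arm, women who drank could have been enrolled at different rates in the two arms. Demographic covariates cannot be relied on to correct an imbalance in drinking itself.

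**Working it through.** The plan gives no figure for the AUDIT-C/biomarker association, so there is none to reproduce; what follows is illustrative.

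**Inputs from the documents.** 8 centres (Randomization and intervention). Outcome rates of "at least 40% in the control group and about 25% (or less) in the intervention group" (Sample size), hence a target difference of 40 − 25 = 15 points.

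**Assumptions, not in the documents.** Correlation r between early drinking and outcome of 0.1, 0.3 or 0.5; m = 30 women per centre; ICC of 0.01 or 0.05; 4 centres per arm with equal numbers; early drinking prevalence of 40%, borrowed from the control-group figure. The 240 in the Sample size section counts exposed children, so 240/8 = 30 is not a documented centre size.

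**1. Precision.** Relative to independent observations, the variance is m·ICC + (1 − ICC). If the covariate explains only within-centre variance, this becomes m·ICC + (1 − ICC)(1 − r²). The SE ratio is the square root of the second over the first.

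| ICC | r | Before | After | SE ratio | Fall in SE |
|---|---|---|---|---|---|
| 0.01 | 0.1 | 1.290 | 0.30 + 0.99×0.99 = 1.280 | 0.996 | 0.4% |
| 0.01 | 0.3 | 1.290 | 0.30 + 0.99×0.91 = 1.201 | 0.965 | 3.5% |
| 0.01 | 0.5 | 1.290 | 0.30 + 0.99×0.75 = 1.043 | 0.899 | 10.1% |
| 0.05 | 0.1 | 2.450 | 1.50 + 0.95×0.99 = 2.441 | 0.998 | 0.2% |
| 0.05 | 0.3 | 2.450 | 1.50 + 0.95×0.91 = 2.365 | 0.982 | 1.8% |
| 0.05 | 0.5 | 2.450 | 1.50 + 0.95×0.75 = 2.213 | 0.950 | 5.0% |

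Ignoring centres altogether, √(1 − r²) = 0.995, 0.954, 0.866, a fall of 0.5, 5 or 13%.

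**2. Selective recruitment, if it occurred.** Suppose MI centres enrol drinkers at 80% of the rate for non-drinkers. Early drinking among enrolled MI women is then 0.4×0.8/(0.4×0.8 + 0.6) = 34.8%, a shift of 5.2 points. Multiplied by r, the unadjusted risk difference is biased by 0.5, 1.6 or 2.6 points in favour of MI, against the 15-point target. Adjusting for accurately reported drinking removes this.

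**3. What self-report does to the remedy.** These figures use a linear model of outcome on arm and reported drinking, with no MI effect.

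- Equal under-reporting in both arms of 5, 10 or 20 of the 40 points, with recruitment as in step 2: 19%, 35% or 62% of the bias remains.
- Controls alone under-report by 5 points, no selection: reported drinking is 40% in the MI arm and 35% in controls. The pooled slope is r×(0.24 + 0.21)/(0.24 + 0.2275) = 0.963r. The adjusted estimate is off by 0.963r×5 = 0.5, 1.4 or 2.4 points in favour of MI, where the unadjusted estimate is unbiased.
- Break-even in the step 2 scenario, with MI women reporting accurately: once controls under-report by 5.2 points, reported drinking is the same in both arms and adjustment no longer helps.

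**4. Order of AUDIT-C and MI.** If the first session came before AUDIT-C and lowered drinking at that point by 5 points (assumed), adjustment would remove about r×5 = 0.5, 1.5 or 2.5 points of genuine effect, about as large as the recruitment bias in step 2.

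**5. Scale.** With 40% v 25% and no imbalance, the marginal odds ratio is (0.25/0.75)/(0.40/0.60) = 0.50. Conditional on early drinking it is 0.50, 0.47 or 0.41 for r = 0.1, 0.3, 0.5. The odds ratio moves on adjustment even with balanced arms, so adjusted and unadjusted results should be compared as risk differences.

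**The case against.** The strongest reply is that this is a covariate choice in a supplementary model, with unknown prognostic value and a measure whose timing is unclear. Much of that stands.

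- The documents do not call AUDIT-C a baseline measure. They place it in the first trimester, as they do an MI session. It is a valid adjustment covariate only if it comes first.
- The plan uses the word demographic loosely: its list includes BMI and is left open, and the habits questionnaire might also record drinking. But an open list does not make a drinking score a planned covariate; it leaves the choice until after the data are seen.
- A reader might infer a precision gain of up to 13%. That figure ignores the centres; step 1 gives the smaller gains. The gain would be larger if AUDIT-C explained differences between centres, but the documents are silent on that.
- The gain concerns the risk difference, whereas the quoted model yields an odds ratio. It materialises only if an adjusted risk difference is added.
- The illustration uses yes/no drinking rather than the AUDIT-C score, and models selection in one direction only. Under-enrolment of drinkers in control centres would bias against MI.

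The reply does not remove the point. An early measure of the outcome behaviour is already collected, and the only adjusted model does not name it.

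**Conclusion.** The point holds as a modest, inexpensive improvement, conditional on AUDIT-C being completed before MI starts. The SE of the risk difference would fall by about 3.5 to 10% at ICC 0.01 and 2 to 5% at ICC 0.05 for r of 0.3 to 0.5, and by almost nothing at r = 0.1, all on the assumed 30 women per centre and within-centre variance only.

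A reader might infer that the omission biases the primary comparison. It does not: allocation was random, so the unadjusted contrast is unbiased on average with respect to early drinking unless recruitment was selective, and chance imbalance is ordinary sampling error. A reader might also infer that recruitment was selective. The documents make this possible but do not show it, so the 0.5 to 2.6 points in step 2 size a scenario and are not an estimate. Nor does adjustment dependably cure such bias: it removes only part under equal under-reporting and can add bias if disclosure differs by arm.

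The lack of any cluster term in the Statistical analysis section is a separate issue and adds no weight here.

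**What to change.** - Keep the unadjusted risk difference as planned.
- Add the first-trimester AUDIT-C score to the adjusted model, with a short fixed list of demographic covariates in place of the open one.
- Report an adjusted risk difference beside the odds ratio, with inference that respects the 8 centres.
- State that AUDIT-C is completed before the first MI session and administered in the same way in both arms. Check dates for women already enrolled. If scores were taken after MI began, treat the adjusted result as a sensitivity analysis only.
- Do not adjust for the post-delivery AUDIT-C score, which MI could have changed.
- Tabulate first-trimester AUDIT-C by centre and arm, and report how many women lack a score and so leave the adjusted model.
- Show both estimates and discuss any disagreement.

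**Cost.** No new data: one covariate and a fixed list, programming of an adjusted risk difference suited to 8 centres, a line on timing and administration, a date check and one table. The downside is reliance on self-report. A 5-point disclosure gap between arms could add about 1.4 to 2.4 points of bias at r of 0.3 to 0.5, which is why the unadjusted estimate must stay beside the adjusted one.
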